1 BACKGROUND

1.1 CANCER OF THE ORAL CAVITY

Cancer of the head and neck is the sixth most prevalent cancer worldwide, with an incidence exceeding half a million cases annually.¹ The most recent data from the NCI Surveillance, Epidemiology, and End Results (SEER) Program predicted that 48,330 men and women (34,780 men and 13,550 women) would be diagnosed with and 9,750 men and women would die of cancer of the oral cavity and pharynx in 2016.² These numbers represent an estimated 16.8% increase in the incident and 23.57% in death rate when compared to the published statistics in 2013 (41,380 were diagnosed and 7,890 were expected to die from head and neck cancer).³ The steady increase in incidents and death rate suggest that there is an urgent need to improve the treatment for this specific cancer.

1.2 STANDARD TREATMENT FOR EARLY STAGE CANCER OF THE ORAL CAVITY

Surgery and radiotherapy are standard treatment modalities for T1/T2 oral cavity cancer (OCC).⁴ Several studies demonstrated that surgery is the preferred treatment for oral squamous cell carcinoma (SCC), yielding superior 5-year survival rates when compared to radiation therapy.^{4,5} Furthermore, the sequelae of radiation therapy such as xerostomia, chronic dental decay and risk of mandibular osteonecrosis remain long after the patient is “cured,” reducing the patients’ quality of life (QoL).⁶

Effective surgical treatment of OCC requires wide local resection of the primary tumor with clear surgical margins. In order to secure tumor free margins the surgical procedures remove additional functional tissue often affecting speech and swallowing. **Following the initial surgery, the risk of local recurrences is as high as 20%.**⁷⁻⁹ Local recurrences are usually treated with further surgery, requiring more mucosal resection. Patients that have been cured with standard therapy also have a significant risk of developing second primary tumors, which has been associated with poor prognosis.¹⁰⁻¹² Treatment of second primaries will increase patient morbidity. Currently, younger patients are being diagnosed with oral cancer, and their QoL is severely affected by standard of care therapies.^{6,13} It is important to provide this patient population with a first line therapy that will not cause irreversible long-term toxicities, and if failed, can be followed with standard surgery to improve the chance of cure.

Photodynamic therapy (PDT) can result in good local control of early stage OCC with minimal loss of tissue volume and excellent long-term healing that is expected to improve QoL.¹⁴⁻¹⁶ Our experience (including our collaborator, [name]) suggest that patients who failed to respond to PDT can be safely salvaged with standard surgery.^{17,18}

1.3 PHOTODYNAMIC THERAPY FOR EARLY STAGE HEAD AND NECK CANCER

Numerous studies over the past 25 years have used photodynamic therapy (PDT) to treat early stage oral and oropharyngeal carcinomas. While many of the early studies were single site with small numbers of patients, in 2004 a major prospective multi-center trial was conducted using mTHPC-PDT to treat early (carcinoma in situ, Cis -T2) disease.¹⁹ A total of 114 patients were

treated with an overall complete tumor response (CR) of 85% which was maintained in 85% of the patients for 1 year. In 2010 Biel reported the cumulative results of treatment of Cis-T1 carcinomas with Photofrin-PDT to be a CR of 94% with a 5 year response of 90%.²⁰ A review of the literature showed that, between 1990 and 2013, 729 patients were treated with PDT with a cumulative overall tumor response rate of 0.85 (Table 1). Importantly, healing was reported to be excellent and salvage treatment carried out by either surgery or repeated PDT resulted in 100% CR.²⁰ Side effects were largely limited to photosensitivity and pain at the treatment site, which was easily managed by analgesics. Photosensitivity was more pronounced and last longer when Photofrin was used;²⁰ however second generation photosensitizers, mTHPC and HPPH, resulted in only mild-moderate photosensitivity.²¹ Importantly, several studies have shown that PDT results in fewer treatment-associated morbidities than conventional therapies, including little to no nerve damage, minimal scarring and retention of organ function.¹⁸⁻²² The organ sparing nature of PDT has the potential to result in fewer complex reconstructive surgical interventions.

Although no direct comparison studies showing superiority or at least non-inferiority to the standard of care (SoC) modalities of surgery or radiotherapy have been conducted, single site and retrospective studies have compared responses after PDT vs. surgery in early stage oral cancer. Karakullukcu et al.²³ found no significant difference in treatment outcome between PDT (n=55) and surgical removal (n=43) of T1s-T2 oral cancer. A multicenter retrospective meta-analysis of 126 PDT and 56 surgical T1 cases demonstrated a comparable CR and no significant differences in overall survival were observed between the two modalities.²⁴

1.4 PRECLINICAL STUDIES WITH HPPH

A detailed discussion of the preclinical pharmacology, pharmacokinetics, and toxicology of HPPH can be found in the Investigator's Brochure.

1.5 CLINICAL STUDIES: HPPH

1.5.1 PHARMACOKINETICS (PK)

A detailed description of the PK studies, results and analysis, can be found in section 5.2 of the Investigator Brochure.

One study in 25 cancer patients revealed estimated mean population α and β half-lives (95% confidence intervals) of 7.77 hours (3.46 - 17.6 hours) and 596 hours (120 - 2951 hours), respectively.⁴¹ No metabolites were detected in serum. A more extensive study of skin photosensitivity in 48 patients receiving HPPH doses of 2.5 - 6 mg/m² and solar simulator light doses from 44.4 - 133.2 J/cm² demonstrated that one day after drug administration the highest drug and light doses elicited a response of only erythema without edema. With over 70 patients treated to date we have found that (a) HPPH at doses of 2.5 - 6 mg/m² has no systemic toxicity; (b) HPPH at doses of 3 mg/m² and higher (to 6 mg/m²) approaches the effectiveness of Photofrin® (no head to head comparisons have yet been carried out), and (c) HPPH does not induce long-term cutaneous photosensitivity, based on in-house solar simulator testing and patient input.

1.5.2 THE HPPH DOSE

In this protocol the participants will be treated with HPPH at fixed dose of 4 mg/m². This dose is based on 5 studies, balancing safety and efficacy considerations, where HPPH-PDT was employed in the treatment of esophageal cancer - 2 studies in obstructing disease and 3 studies in high grade dysplasia, CIS and early adenocarcinoma. The number of patients enrolled per HPPH dose was as follows: 11 at 6 mg/m², 3 at 5 mg/m², 36 at 4 mg/m² and 32 at 3 mg/m². All were treated with 150 Joules/cm². The percentages of SAEs possibly, probably and definitely related to PDT were in order 46%, 33%, 28% and 28%, respectively. Additionally, in the studies of high-grade dysplasia, CIS and early adenocarcinoma, 72% of complete responses were observed at 1 year at 3 and 4 mg/m² combined, while no complete responses were observed at 5 or 6 mg/m². There was no statistical difference in outcomes between 3 and 4 mg/m² (Nava et al., *Lasers in Surg. Med.* 43, 705-12, 2011).⁴² The latter is likely due to photochemical oxygen depletion in tissue with high photosensitizer levels, which limits photodynamic action.

1.5.3 THE LIGHT FLUENCE RATE AND DOSE FOR EARLY STAGE HEAD AND NECK CANCER

Recently, RPCI has completed 3 Phase I studies of PDT with HPPH in the treatment of HNSCC. In the first study, (NCT00670397) PDT with HPPH was used intra-operatively in patients with resectable, primary or advanced recurrent SCC of the head and neck.⁴³ This was a dose escalation study, where the drug dose was 4 mg/m² and light dose was increased from 30 - 75 J/cm². In this study, no serious adverse event was reported. The treatment was found to be safe at the maximum light dose of 75 J/cm². Furthermore, major neurovascular structures and blood vessels were irradiated with the laser light during the PDT, but no carotid artery ruptures or cranial nerve injuries were observed, demonstrating that PDT with HPPH does not induce irreversible damage to healthy vital structures. This study also observed excellent healing of the overlaying skin in the 2 subjects that experienced skin burns as an adverse event. This healing was attributed to the fact that HPPH is not transported into fibroblasts.⁴⁴ Thus, the native tissue that replaces the cancer cells regains its normal functions, significantly limiting function loss and minimizing scar formation.

1.6 RISKS AND/OR BENEFITS

For participants that will have partial or complete response to PDT, the potential benefits include complete clinical regression of the tumor. Participants that do not respond to PDT may not benefit from this treatment. There is no guarantee of the outcome nor is it possible to predict whether or not the participant will respond to HPPH mediated PDT.

This is a Greater Than Minimal Risk study according to IRB criteria. The most likely potential risks associated with the PDT are short term edema and pain.

2 RATIONALE

Surgical resection and radiotherapy are front line therapies for T1 and T2 oral cavity cancer. However, these therapies are associated with multiple morbidities and impaired QoL issues such as alteration of speech, dysphagia and xerostomia. PDT, which involves the activation by light of

a tumor-localized photosensitizer, has proven to be an effective local treatment for a range of solid tumors. It has the potential to become an effective first line treatment modality for this disease for the following reasons: it is minimally invasive, has low toxicity, is not associated with any long-term morbidity and is repeatable. Importantly, it allows the physician to reserve conventional, more toxic treatments such as radiotherapy and chemotherapy for later application, if needed.

The purpose of this multicenter study is to test the non-inferiority of PDT with HPPH to standard of care by comparing the rate of tumor response and QoL after PDT to those obtained after surgery in participants with previously untreated T1/T2 N0 SCC of the oral cavity.

Phase I studies have demonstrated that this treatment is safe. These studies also determined the safe drug and light dosages: 4 mg/m² and 100 - 140 J/cm², respectively. Data also suggest that early stage SCC may have excellent response to this therapy (see **Table 1**).

In our recent study with HPPH-PDT, all the patients with T1/T2 who failed to have CR to PDT were successfully salvaged with surgery.¹⁸ Importantly, in patients with invasive disease who achieved only PR, the disease could be downgraded to dysplasia, thus minimizing salvage surgery. While all studies with HPPH-PDT to date have been Phase I studies, the response to PDT is swift and all patients, with few exceptions, have been assessed for response by pathological analysis.

We believe that PDT with HPPH is a viable option to treat patients with T1/T2, because:

- HPPH-PDT is expected to be an organ sparing treatment option, and failures can be salvaged with surgery.
- HPPH, at clinically effective antitumor doses, is associated with significantly reduced cutaneous photosensitivity that rapidly declines over several days.⁴¹
- The CR to HPPH-PDT is expected to be 85%, which would be comparable to cure rates after the initial surgery that is associated with 20% local recurrence.⁷⁻⁹
- Noninvasive optical spectroscopy has potential to serve as a surrogate reporter for tumor response to HPPH-PDT.⁴⁸

Therefore, we hypothesize that patients may choose a treatment option, such as PDT with HPPH, if it provides non-inferior cure rate at the time of the initial treatment.

2.1 RATIONALE FOR ANCILLARY LABORATORY STUDIES

In the current study, immune cells will be collected from participants before and after PDT and tested for reactivity to the participant's tumor cells. These will only be collected from participants randomized to PDT with HPPH. Refer to **Appendix G**.

3 OBJECTIVES

3.1 PRIMARY OBJECTIVE

- To test the non-inferiority of PDT to standard of care surgery by comparing the rate of tumor response after PDT to those observed after surgery, at 24 months post treatment.

3.2 SECONDARY OBJECTIVES

- To determine quality of life (QoL) at 6, 12, 18, and 24 months post PDT or surgery.
- To assess the toxicity using the CTEP NCI Common Terminology Criteria for Adverse Events (CTCAE Version 4.0).

3.3 TERTIARY OBJECTIVE

- Immune markers (T cells).
- To investigate the correlation of the diffuse reflectance optical spectroscopy with tumor response to PDT (**Appendix B**).

4 METHODOLOGY

[figure not shown]
4.1 STUDY DESIGN

This is an open-label, randomized, multicenter Phase II study of HPPH-mediated PDT in participants with lesions that are diagnosed as previously untreated T1 N0 or T2 N0 SCC of the oral cavity. Participants will be randomized at a ratio of 1:1, to be treated with either surgery (57 participants) or PDT with HPPH (57 participants). The randomization will be done at RPCI by the biostatistician. The study schema is depicted in **Figure 1**.

Participants will be treated on an outpatient basis. Rarely, those undergoing HPPH with PDT may require hospitalization but this will be decided on a case by case basis. Participants undergoing surgery may be hospitalized.

4.1.1 Treatment Procedure

Figure 1. Study Schema

For those participants randomized to HPPH with PDT, a single dose of HPPH at 4 mg/m² will be administered via slow intravenous (IV) infusion over 1 hour. Approximately 24 hours (\pm 4 hours) later, the target tumor will be illuminated with a 665 \pm 3 nm laser (ML7710-665 LASER, Modulight, Inc., Tampere, Finland). A total light dose of 140 J/cm² at a fluence rate of 150 mW/cm² will be delivered with a single quartz fiber optic equipped with a micro lens (Frontal Light Distributor Model FD1, Medlight SA, Switzerland). In areas that preclude direct illumination of the lesion and margins with a microlens fiber, the light will be delivered through a cylindrical diffuser fiber with a diffuser end (Medlight SA, Switzerland) that will be inserted into a 10 mm in diameter flexible applicator (Frieburg Flap, Elekta Inc. Atlanta, GA). The Frieburg Flap is an FDA approved device designed to keep radiation source at constant distance from the treatment surface (see attached letter of approval). Multiple cylindrical fibers (in parallel) can be inserted into the flap to cover an entire tumor and margins in curved surfaces. The light through each cylindrical diffuser will be delivered at a fluence rate of 495 mW/cm (accounting for about 5% loss) to a total light dose of 462 J/cm, which is equivalent to surface illumination of 150 mW/cm² and 140 J/cm². The PDT center at RPCI will provide sections of the Frieburg Flap that will need to be sterilize prior to use, following the manufacturer instructions (see attached). The entire tumor and 5 mm - 10 mm margins will be illuminated. The remainder of the oral cavity will be shielded to avoid illumination of healthy tissue.

4.1.2 Post Treatment Evaluation

Participants will be scheduled to have a clinical examination at 1 week and within 4 - 6 weeks and at 12 – 16 weeks post therapy. In the event that a suspicious lesion is observed, participants will be scheduled for a biopsy at the discretion of the treating physician, at 4-6 weeks post treatment. In addition, a scheduled pathological evaluation will be conducted by taking a 3-mm punch biopsy from the treated tumor site during the clinical visit at 12-16 weeks post therapy.

Tumor response will be determined at 24 months post treatment. The treating physician will examine the clinical response and a photograph of the treatment site will be taken with paper ruler, to determine the reduction in the lesion size, according to RECIST v1.1. A biopsy may be taken, if clinically indicated. The biopsies will be processed following the standard of care pathology. A clinical pathologist will examine the processed tissue section and determine the pathological response.

Participants who have partial or no-response will be offered standard therapy, at the discretion of the treating physician.

We hypothesize that non-responders or partial responders in the PDT arm are likely to be participants whose tumor does not retain HPPH. For this subset of participants that are treated with PDT at RPCI, an additional biopsy (50 mg tissue mass) will be taken at the time of excision of the recurrent tumor to evaluate cellular mechanisms that contribute to tumor retention of HPPH. The biopsy sample is immediately dropped into a sterile 15-ml screw-cap tissue culture tube containing 5 ml of serum-free RPMI medium. A set of such tubes are prepared prior to surgery and can be stored at 4°C for up to a month until use. A research nurse (or other personnel in the operating room, OR) will label the sample tube with an identifier code pertaining to the case, but without inclusion of any PHI. The tube containing the biopsy sample will be placed either into a refrigerator or bucket of ice until pick-up by a member of the investigating laboratories (Drs. [name] or [name], as detailed below). The OR personnel will inform the research associate in the laboratories of either [name] or [name] via telephone or text message. The

associate will pick-up the sample tube at the entrance to the OR and immediately carry it to the laboratory of [name], or [name].

The analysis will be performed in vitro by generating primary tumor cell culture from the biopsy material. The tumor cells will be incubated with HPPH and uptake and retention monitored over 72 hours in the live cultures by microscopic imaging. HPPH fluorescence will serve as indicator for subcellular location and concentration of HPPH.

Contact person in [name] laboratory:

[name]
Research Associate
Department of Molecular and Cellular
Biology
Roswell Park Cancer Institute
[name]
[name]
[contact] (Office),
[contact]

Contact person in [name] laboratory:

[name]
Research Technologist
Photodynamic Therapy Center
Department of Cell Stress Biology
Roswell Park Cancer Institute
[name]
[name]
[contact] (Office)
[contact]

4.2 PARTICIPANT QUALITY OF LIFE EVALUATION

Participants' QoL will be evaluated with the widely accepted University of Washington Quality of Life Questionnaire Version 4 (UW-QoLQ v4).^{49,50} It has been tested in several prospective studies and found to be reproducible, reliable, and valid for head and neck cancer patients.⁵¹ It is simple to complete, employs a simple algorithm to compute the overall score, and is easy to interpret while yielding objective results.⁵¹ This version includes 12 individual Likert-scale items and 4 global questions. Each participant's overall score on the UW-QoLQ v4 will be calculated at baseline, at 12-16 weeks, and at 6, 12, 18, and 24 months post-PDT.

4.3 MANAGEMENT OF THE NECK AND SALVAGE SURGERY

The management of the neck will be according to standard of care, at the discretion of the treating surgeon. If the participant, based on the pathology of the neck dissection or primary oral cancer resection, has perineural invasion, extracapsular spread, or requires additional therapies including radiation or chemotherapy, they will be dropped from the study and replaced with another participant.

Participants will receive standard curative therapy 6 weeks after failing to respond to PDT with HPPH. All the participants who will have disease progression, local recurrence, or partial or no response (PR, NR) following the PDT with HPPH will be considered treatment failures. The determination will be performed during the study visits, and based on clinical exam and pathology, if clinical exam is unclear.

The surgeon will provide a surgical plan for every patient, including those randomized to PDT. If the patient requires salvage surgery post-PDT, the surgeon will compare the salvage surgery specimen diameter to the diameter of the spot size used for PDT. This data will be used to demonstrate whether PDT affects the surgical plan.

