5.2 EXCLUSION CRITERIA

Participants will be excluded from this study for the following:

1. Those who have had chemotherapy or radiotherapy or targeted agents within 4 weeks (6 weeks for nitrosoureas or mitomycin C) prior to entering the study or those who have not recovered from adverse events due to agents administered more than 4 weeks earlier.
2. Those with known brain metastases should be excluded from this clinical trial because of their poor prognosis and because they often develop progressive neurologic dysfunction that would confound the evaluation of neurologic and other adverse events.
3. Those with porphyria or with known hypersensitivity to porphyrins or porphyrin-like compounds.
4. WBC < 4,000.
5. Those with impaired renal and/or hepatic function (total serum bilirubin >2 mg/dL, serum creatinine > 2 mg/dL, alkaline phosphatase (hepatic) or SGOT > 3 times the upper normal limit.
6. Diagnostic biopsy reveals perineural invasion (PNI) and/or lymphovascular invasion (LVI).
7. Uncontrolled intercurrent illness including, but not limited to, ongoing or active infection, symptomatic congestive heart failure, unstable angina pectoris, cardiac arrhythmia, or psychiatric illness/social situations that would limit compliance with study requirements.
8. Nodal disease as detected by clinical exam or CT.
9. Pregnant or nursing females.
10. Unwilling or unable to follow protocol requirements.
11. Any condition which in the Investigator's opinion deems the participant an unsuitable candidate to receive study drug.
12. Received an investigational agent within 30 days prior to enrollment.
13. Trismus or compromised airway.
14. Previous treatment in the target tumor area.

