7.4 STUDY WITHDRAWAL

Upon participant withdrawal from the study, all end of study evaluations and tests will be conducted. All participants who discontinue due to an AE must be followed until the event resolves or stabilizes. Appropriate medical care should be provided until signs and symptoms have abated, stabilized, or until abnormal laboratory findings have returned to acceptable or pre-study limits. The final status of the AE will be reported in the participant's medical records and the appropriate eCRF.

Reasons for study withdrawal should be classified as follows:

- Death.
- Progressive disease.
- Treatment-related toxicity.
- Toxicity unrelated to treatment.
- Investigator judgment.
- The Investigator may withdraw a participant if, in his/her judgment, it is in the participant's best interest to do so.
- Participant receives an additional adjuvant therapy.
- Noncompliance
- Participant voluntary withdrawal
- A participant may withdraw from the study at any time, for any reason. If a participant discontinues treatment, an attempt should be made to obtain information regarding the reason for withdrawal.
- Participants in which the surgical pathology demonstrates perineural invasion, extracapsular spread or the participant requires additional therapy including radiation or chemotherapy.

Participants who are unavailable for follow-up evaluations should be classified as lost to follow-up for 1 of the following reasons:

- Lost to follow-up: For a participant to be considered lost to follow-up, the investigator must make two attempts to re-establish contact with the participant. The attempts to re-establish participant contact must be documented (e.g., certified letter).
- Death: Date and cause of death will be recorded for those participants who die within 30 days after last dose of study drug (telephone contact with family is acceptable).

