8.1 PARTICIPANT RANDOMIZATION AND REGISTRATION

We will employ a web-based stratified blocked randomization scheme developed at RPCI by the biostatistician in conjunction with the GOG Foundation Statistical & Data Management Center. Participants will be randomized stratified by study site with permuted blocks of size 4 within strata and will assigned to standard of care surgery or PDT with HPPH. Study sites will need to have IRB approval entered into the system prior to accessing the randomization system. Eligibility of each participant will be established prior to randomization.

Informed consent **MUST** be completed prior to receiving any study related procedures.

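### Section 4.3 drops and replaces randomised participants on post-randomisation pathology, so the intent-to-treat analysis in 12.2–12.3 cannot be carried out within the cap of 114

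*Combined protocol and SAP*

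**What the plan says.** Section 4.3 (Management of the Neck and Salvage Surgery) applies to a participant whose neck-dissection or primary-resection pathology shows perineural invasion or extracapsular spread, or who "requires additional therapies including radiation or chemotherapy, they will be dropped from the study and replaced with another participant". The same section says that progression, local recurrence, and "partial or no response (PR, NR) following the PDT with HPPH will be considered treatment failures". It gives no matching failure rule for surgery.

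Section 7.4 lists as withdrawal reasons "Participants in which the surgical pathology demonstrates perineural invasion, extracapsular spread or the participant requires additional therapy including radiation or chemotherapy" and "Participant receives an additional adjuvant therapy". It does not mention replacement. It adds: "Upon participant withdrawal from the study, all end of study evaluations and tests will be conducted".

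These triggers arise after allocation. Section 8.1 states: "Eligibility of each participant will be established prior to randomization". The related exclusion in 5.2 covers only what the initial sample shows: "Diagnostic biopsy reveals perineural invasion (PNI) and/or lymphovascular invasion (LVI").

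On the analysis side:
- Section 12.2 places participants in the arm to which they were randomised, whatever they received. The one exception it names is consent to data use withdrawn before study medication.
- Section 12.2 also rules out imputation.
- Section 12.3 and the synopsis make all randomised participants evaluable for response.
- Section 4.4 sets a maximum of 114, and section 4.1 allocates all of them, 57 to each arm.

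**The concern.** The operational sections remove people whom the statistical sections require to be counted. The plan does not say how a dropped participant's 24-month response is scored, which arm a replacement joins, or whether replacements count toward 114.

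Removal is also tied partly to the assigned treatment. Every surgery participant has a primary-resection specimen as part of the assigned treatment. A PDT participant has one only at salvage, if 4.3 is meant to cover that case at all. Neck dissection can occur in both arms. Exclusion can therefore differ between arms for reasons linked to treatment and prognosis, and randomisation no longer protects the primary comparison.

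The trial is open-label. If the handling of these participants is settled after outcomes are known, the result could influence the choice.

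**Working it through.** **1. Can the rules be followed together?**

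| Rule | Where | Effect of a drop under 4.3 |
|---|---|---|
| Analyse as randomised | 12.2 | The participant must be analysed but has left the study |
| All randomised evaluable | 12.3, synopsis | An evaluation made at withdrawal is not the 24-month response |
| No imputation | 12.2 | The missing 24-month response cannot be filled in |
| Maximum 114 | 4.4, with 57 + 57 in 4.1 | 57 + 57 = 114 leaves no reserve; one replacement that restores 57 + 57 gives 115 |

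If intent-to-treat governs, the dropped person still counts and the replacement has no purpose. If replacement governs, the analysis is not intent-to-treat.

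**2. The plan's own power figure.** Inputs from 12.2: Farrington-Manning test, margin 0.20, 85% response in both arms, 57 per arm, level 0.05, about 80% power. The sidedness of this test is not stated. I assume one-sided 0.025. The restricted null rates are 70.8% and 90.8%.
- Null SE = √[(0.708×0.292 + 0.908×0.092)/57] = 0.0714
- Alternative SE = √[2×0.85×0.15/57] = 0.0669
- Power = Φ[(0.20 − 1.96×0.0714)/0.0669] = 81.5%

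Exact enumeration gives 83.2% power, and 2.6% type I error at 65% against 85%. At one-sided 0.05 the power would be 89.1% (exact 89.8%), so the plan's figure fits one-sided 0.025.

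**3. Can the handling of dropped participants change the conclusion?** The counts are assumed: PDT 43/57 (75.4%); surgery 57 randomised, 6 dropped, 45 of the other 51 respond. The statistic is Z = (PDT rate − surgery rate + 0.20) / restricted SE.

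| The 6 dropped are | Surgery | Difference | Z | One-sided p |
|---|---|---|---|---|
| excluded | 45/51 = 88.2% | −12.8 points | 0.986 | 0.162 |
| kept as non-responders | 45/57 = 78.9% | −3.5 points | 2.086 | 0.0185 |
| kept as responders | 51/57 = 89.5% | −14.0 points | 0.842 | 0.200 |

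The same patients pass or fail depending on an unstated choice. The pattern is the same at one-sided 0.05.

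**4. Direction of bias.** Let q be the share dropped and f the share of those who would fail; both are assumed. The retained rate is (0.85 − q(1−f))/(1−q). Results are exact, one-sided 0.025, with 57/57 after replacement.
- Surgery drops only, f = 40%: at q = 5% the retained surgery rate is (0.85 − 0.03)/0.95 = 86.3% and power is 79.1%. At q = 20% it is (0.85 − 0.12)/0.80 = 91.3% and power is 58.0%.
- Surgery drops only, f = 15%: the retained rate stays at 85% and power at 83.2%.
- Surgery drops only, f = 5%: type I error rises to 3.0% (q = 5%) and 5.1% (q = 20%).
- Equal drops in both arms, f = 40%: power rises to 85.5% (q = 5%) and 93.6% (q = 20%).

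These figures hold the PDT arm at 57. Section 8.1 says "Participants will be randomized stratified by study site with permuted blocks of size 4 within strata", so refilling surgery through the randomisation would enlarge PDT too. At q = 20% surgery needs 57/0.80 ≈ 71 randomised, and PDT would also reach about 71. With 71 against 57 analysed, power is 66.9% at f = 40% and 87.8% at f = 15%. That is a different trial, and the two sets of figures should not be combined.

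**The case against.** The strongest defence is that 12.2 and 12.3 do name the analysis set, while 4.3 and 7.4 are operational and never mention analysis. On that view, dropped means only off study, and intent-to-treat still governs. This narrows the point. A reader might infer that the plan leaves the analysis set undefined, and the documents do not support that: the set is named, but 4.3 and 7.4 prevent it from being carried out. The defence does not remove the conflict, because the 24-month outcome is still not assured, replacement is still unexplained and the cap is still exceeded. The list of exceptions in 12.2 is not worded as exhaustive, but no section names pathology as an exception.

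A reader might also infer that the rule must favour one arm. The documents give no drop rate for either arm and no outcome for those dropped, and 5.2 already excludes tumours with perineural or lymphovascular invasion on the diagnostic biopsy. Surgery-only drops can lower power or raise type I error, and equal drops in both arms can raise power.

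A third tempting inference is that a later drop at salvage erases a recorded PDT failure. Section 4.3 counts all such participants as failures, so that reading is disfavoured and I place no weight on it.

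It is fair to add that the other withdrawal reasons in 7.4 also leave 24-month outcomes in doubt. That is a wider missing-data question than this one.

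**Conclusion.** The concern holds as a contradiction that must be resolved before the primary analysis. The drop-and-replace rule in 4.3, with the matching withdrawal items in 7.4, cannot be followed alongside intent-to-treat, evaluability of all randomised participants, the bar on imputation and the maximum of 114. This conclusion rests on the text alone and needs no assumed rate.

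The size is illustrative. With 6 of 57 surgery participants affected, the p-value ranges from 0.0185 to 0.200 according to how they are handled. With 5–20% surgery-only drops, 40% of whom would fail, power falls from 83.2% to between 79% and 58%. With equal drops in both arms it rises, to 93.6% at 20%. All counts, drop rates, failure rates and the one-sided 0.025 level are assumptions. The net direction of bias is unknown.

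**What to change.** Reconcile 4.3, 4.4, 7.4, 12.2 and 12.3 as follows.

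- Delete the drop-and-replace clause in 4.3.
- State in 7.4 that the surgical-pathology and adjuvant-therapy items end neither follow-up for the primary endpoint nor inclusion in its analysis.
- Follow all randomised participants (maximum 114, no replacements) to 24 months, subject to consent, and analyse them in the assigned arm.
- Apply the failure definition in 4.3 to both arms. A recorded failure stands whatever therapy follows.
- Score a participant who receives adjuvant therapy without failure by observed 24-month status in the assigned arm. This follows the intent-to-treat rule in 12.2. It has to be written down, because step 3 of the working shows that this choice can decide the result.
- Report two labelled sensitivity analyses: one excluding these participants and one counting them as non-responders.

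The cost is a wording amendment, continued follow-up of participants already randomised, and possible re-contact of any already dropped. No patients are added and clinical care is unchanged.
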